#### 4. SUBJECT ELIGIBILITY CRITERIA

This study can fulfill its objectives only if appropriate subjects are enrolled. The following eligibility criteria are designed to select subjects for whom participation in the study is considered appropriate. All relevant medical and nonmedical conditions should be taken into consideration when deciding whether a particular subject is suitable for this protocol

#### 4.1. Inclusion Criteria

Subjects must meet all of the following inclusion criteria to be eligible for enrollment in the study:

1. Males willing to use an acceptable method of contraception and females of non-childbearing potential, age 40 to 75 years (inclusive)

NOTE:

Male patients with a female spouse/partner of childbearing potential or a pregnant or breastfeeding spouse or partner must agree to use barrier contraception (male condom) during the Treatment Period and for at least 7 days after the last dose of KA34. Barrier contraception is required even with documented medical assessment of surgical success of a vasectomy.

Female subjects must satisfy one of the following criteria to be considered of non-childbearing potential:

- a. Achieved postmenopausal status defined as cessation of regular menses for at least 12 consecutive months with no alternative pathological or physiological cause and a serum follicle-stimulating hormone (FSH) level consistent with a postmenopausal state
- b. Have undergone a documented hysterectomy and/or bilateral oophorectomy
- c. Have medically confirmed ovarian failure

- d. Have undergone a documented bilateral tubal ligation
- 2. Diagnosis of localized osteoarthritis (OA) of the knee by American College of Rheumatology (ACR) clinical and radiographic criteria
  - NOTE: Radiographs to confirm the OA diagnosis must be acquired within 6 months prior to Screening
- 3. Evidence of a personally signed and dated informed consent document indicating that the subject has been informed of all pertinent aspects of the study
- 4. Subject is willing and able to comply with all scheduled visits, treatment plan, laboratory tests, and other study procedures
- 5. Patients with a VAS score of ≥ 40 mm on a 100 mm scale on the index knee determined by the Investigator at Screening

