#### 4.3. Randomization Criteria

Subjects will be randomized into the study once they have completed screening and have satisfied all eligibility criteria. Subjects will be randomized in a 3:1 ratio to receive KA34 or placebo in each dose cohort.

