#### 4.4. Contraception Requirements

All fertile male subjects who are sexually active and at risk for pregnancy with their partner(s) must agree to use a highly effective method of contraception consistently and correctly for the duration of the active treatment period and for 7 days after the last dose of investigational product. The investigator or his or her designee will confirm that the subject has selected an appropriate method of contraception from the permitted list of highly effective contraception methods below and will confirm that the subject has been instructed in its consistent and correct use.

Highly effective methods of contraception are those that, alone or in combination, result in a failure rate of less than 1% per year when used consistently and correctly and include the following:

• Established use of hormonal methods of contraception associated with inhibition of ovulation (e.g., oral, inserted, injected, implanted, or transdermal)

- Correctly placed copper-containing intrauterine device (IUD)
- Male condom or female condom used in combination with a separate spermicide product (i.e., foam, gel, film, cream, or suppository)
- Male sterilization with absence of sperm in the post-vasectomy ejaculate
- Bilateral tubal ligation/bilateral salpingectomy or bilateral tubal occlusive procedure (provided that occlusion has been confirmed in accordance with the device's label)

At each study visit during the active treatment period and for 7 days after the last dose of investigational product, the investigator or designee will remind fertile, male subjects of the need to use highly effective contraception consistently and correctly and document the conversation in the subject's source documentation. In addition, the investigator or designee will instruct the subject to call immediately if the selected contraception method is discontinued or if pregnancy is known or suspected in the subject's partner.

Sexual abstinence, defined as completely and persistently refraining from all heterosexual intercourse, obviates the need for contraception as long as the subject affirms that he remains abstinent during the active treatment period and for 7 days after the last dose of study medication.

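### The male-condom rule in inclusion criterion 1 is not carried into Protocol 4.4 or the contraception checks after dosing

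*Protocol*

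**What the plan says.** **Criterion 1.** The note in Protocol 4.1, repeated in the Protocol Summary, covers men whose partner is of childbearing potential, and also men with a pregnant or breastfeeding partner: "a pregnant or breastfeeding spouse or partner must agree to use barrier contraception (male condom) during the Treatment Period" and for at least 7 further days after the last KA34 dose. Vasectomy does not lift the duty: "Barrier contraception is required even with documented medical assessment of surgical success of a vasectomy".

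**Section 4.4.** The section headed Contraception Requirements defines its population differently: "All fertile male subjects who are sexually active and at risk for pregnancy with their partner(s) must agree to use a highly effective method". Site staff confirm that the man "has selected an appropriate method of contraception from the permitted list of highly effective contraception methods below". The list has five entries:

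1. "Established use of hormonal methods of contraception associated with inhibition of ovulation"
2. a copper IUD
3. "Male condom or female condom used in combination with a separate spermicide product"
4. vasectomy with confirmed absence of sperm
5. tubal ligation, salpingectomy or occlusion

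Abstinence removes the need for contraception. The visit reminder that 4.4 prescribes is addressed to fertile men and concerns highly effective methods.

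**When each rule is checked.** Protocol 4.3 says: "Subjects will be randomized into the study once they have completed screening and have satisfied all eligibility criteria". Eligibility is confirmed at screening (6.1) and again on Day 1 (6.2.1, 6.3.1). After Day 1, each visit with a contraception item has a general reminder of the study's requirements, then a confirmation that highly effective contraception is being or was used, where applicable. The early termination visit (6.4) asks men for confirmation of either a barrier or contraception.

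**The concern.** Criterion 1 tests a promise made at entry. Whether the promise is kept can only be seen after dosing, and the items that look at actual use are worded in the terms of 4.4. A site that follows 4.4 and the visit lists faithfully could accept a method, or record a man as compliant, when he is not doing what criterion 1 committed him to.

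Because criterion 1 reaches vasectomised men and partners who are already pregnant or breastfeeding, it appears meant to limit partner exposure as well as to prevent conception. That is an inference, since the protocol does not state the purpose. Protocol 8.4.2 treats a man's exposure around conception or during his partner's pregnancy as a reportable exposure during pregnancy, although it does not mention condoms.

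This is a first-in-human trial. The toxicology programme described in Protocol 1.2.2 lists single-dose, 5-week repeat-dose and genotoxicity studies, and no reproductive or developmental study.

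**Working it through.** The plan gives no figure to reproduce. The check sets the two rules side by side and then counts.

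**Four cases under each rule**

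| Case | Criterion 1 | Section 4.4 | Visit confirmation |
|---|---|---|---|
| Fertile man, partner with IUD or hormonal method | Male condom required | Met without a condom | Passes |
| Vasectomised man, partner of childbearing potential | Male condom required | Not fertile, so outside the rule, or met by vasectomy as a listed method | Passes or not applicable |
| Man with a pregnant or breastfeeding partner | Male condom required | Partner not named; with a pregnant partner the at-risk wording does not clearly reach him | May be treated as not applicable |
| Fertile man using a male condom without spermicide | Met | Not on the list | Fails if the list is applied literally |

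The mismatch runs both ways, but the first three rows matter more, because there the partner is left without the protection that criterion 1 requires. The first row is the clearest: the man falls squarely under both rules, and they ask for different things.

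**Listed methods that satisfy 4.4 without a condom.** Hormonal and IUD: 2 of 5 without qualification. Adding vasectomy gives 3 of 5, with the caveat that 4.4 opens by addressing fertile men. Tubal ligation is not counted, because such a partner would normally not be of childbearing potential (compare item d of criterion 1 for female subjects).

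**Confirmations after dosing**

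- Single dose (6.2): Days 2, 8, 29 = 3
- Multiple dose (6.3): Days 2, 8, 15, 22, 29 = 5
- Early termination (6.4) = 1
- Total: 3 + 5 + 1 = 9

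Of these, 8 name no barrier, 1 names it only as an alternative, and 0 require a condom.

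**Nominal condom period**

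- Single dose: dose on Day 1, plus 7 days, ends on Day 8. Length 8 − 1 = 7 days.
- Multiple dose: last dose on Day 22, plus 7 days, ends on Day 29. Length 29 − 1 = 28 days.

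The whole period follows the last eligibility confirmation, which is made before dosing on Day 1. That is true of any commitment about behaviour after dosing and is not itself a fault. It does mean that the later confirmations are the only scheduled check of actual use.

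**Men affected.** The documents do not say. The number lies between 0 and about 60, the planned number randomised. The upper end is loose, because women are eligible, and at ages 40 to 75 the true number may be small.

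**The case against.** The strongest reply is that the rules do not conflict. Criterion 1 is an entry condition and 4.4 adds a second requirement for fertile men; a male condom with spermicide, or a condom plus another listed method, meets both. Nothing in 4.4 says it replaces criterion 1. A vasectomised man, or one with a pregnant partner, arguably falls outside 4.4 altogether, so criterion 1 alone governs him. **This stands as far as it goes.** The point is an inconsistency and a gap in verification, and the vasectomy and pregnant-partner cases are differences of scope. It does not answer the case of the fertile man whose partner has an IUD.

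There are also other safeguards. At screening, sites make sure that men are willing to follow the contraception requirements for the whole study (6.1). Subjects are reminded of those requirements after dosing on Day 1 and at the eight later visits, and the general phrase used can include criterion 1. Section 4.4 tells the man to call at once if he stops his selected method. **These reduce the gap but do not close it.** The first tests willingness, the second is a reminder, and the third relies on self-report. The call is not triggered if the IUD was the selected method and the condom was promised separately under criterion 1.

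Finally, the risk is probably low. Animal plasma levels after intra-articular dosing were low with rapid clearance (Protocol 1.2.1), genotoxicity tests were negative (1.2.2), and SAP 15.1 expects no quantifiable parent drug after 4 hours. **This is fair and limits the weight of the point.** Negative genotoxicity tests do not, however, settle the question of fetal exposure.

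**Conclusion.** The concern holds. Criterion 1 requires a male condom for a defined group of men, vasectomy notwithstanding. Section 4.4 accepts at least two methods without one, and none of the nine later confirmations requires one. A man could therefore break the protocol's own partner-protection rule and be recorded as compliant throughout.

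The size is modest. The exposure window is nominally 7 or 28 days, the number of men is unknown and possibly small, and the likely risk is low. No endpoint, analysis set or escalation rule is touched. The spermicide mismatch is minor. The point should be corrected, but it does not threaten the trial's conclusions.

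The verdict assumes that sites apply 4.4 and the visit lists as written. The consent pages and the CRF are not in the reviewed copy. If either carries a specific condom instruction or check, the practical gap would be smaller, though the protocol text would still need aligning.

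**What to change.** - **In 4.4:** state that men with a partner of childbearing potential, or a pregnant or breastfeeding partner, must use a male condom during treatment and for at least 7 days after the last dose, in addition to any listed method and regardless of vasectomy. The abstinence exemption can stay. Say whether spermicide is needed with the condom.
- **In 6.2, 6.3 and 6.4:** have the confirmations ask these men specifically about condom use. A cross-reference in 4.4 alone would align the rules but leave actual use unchecked.
- **If the condom rule is not intended:** relax criterion 1 in the Protocol Summary and 4.1 instead.

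The cost is a wording amendment with IRB/EC approval (Protocol 12.1). The main fix touches four places (4.4, 6.2, 6.3, 6.4) and the alternative touches two. No statistical output changes. Whether the consent form or CRF also needs editing cannot be judged from the documents available.

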#### 6. STUDY PROCEDURES

#### 6.1. Screening (Visit 1)

Subjects will be screened during the 28 days prior to administration of investigational product (Day 1) to confirm that they meet the entry criteria for the study. The investigator or an appropriate designee will obtain informed consent from each subject prior to conducting any study procedures.

The following procedures will be completed during Screening to determine subject eligibility for participation:

- Obtain written informed consent
- Collect demographic information
- Administer VAS pain scale
- Obtain medical history, including any history of illegal drug, alcohol, and tobacco use. Include a history of the subject's OA symptoms and diagnosis.
- Obtain complete history of all prescription drugs, non-prescription drugs, dietary supplements, and herbal supplements taken within the last 30 days. Obtain a history of all previous and current pharmacological treatments for OA and all non-drug treatments for OA within the previous 12 months.
- Conduct full physical examination
- Obtain height and weight
- Obtain temperature and seated blood pressure (BP) and pulse rate (PR)
- Obtain 12-lead ECG
- Review the subject's tibial-femoral radiographs to confirm the diagnosis of OA and determine the Kellgren-Lawrence Grade. If the subject does not have tibial-femoral radiographs of adequate quality that were acquired within 6 months of the anticipated Day 1 date, new radiographs should be obtained.
- Collect blood and urine samples for the following:
  - Safety laboratory tests (hematology, chemistry, and urinalysis)
  - Serum FSH concentration (for female subjects)
  - Urine drug test
- Obtain MRI according to the procedures outlined in the Imaging Manual
- Review contraception requirements and ensure the subject is willing to comply with the contraception requirements throughout the study (for male subjects)
- Confirm and document that the subject satisfies the eligibility criteria

Screening procedures may be completed across multiple days during the 28-day screening period and do not need to be conducted on consecutive days.

Subjects who are screen failures may be rescreened for study participation if deemed appropriate by the investigator.

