#### 6.2. Treatment & Follow-Up Procedures – Single Dose Cohorts

#### 6.2.1. Day 1 (Visit 2)

The following procedures will be completed on Day 1:

- Collect blood and urine samples for safety laboratory tests
- Collect pre-dose PK blood sample
- Collect pre-dose serum sample for PIIANP assessment
- Collect pre-dose urine sample for CTX-II assessment
- Collect pre-dose serum sample for biospecimen banking (if the subject has consented to provide this optional sample)

NOTE: All D1 pre-dose laboratory assessments should be conducted within 48 hours prior to IP administration and other pre-dose assessments conducted within 2 hours prior to IP administration.

- Administer WOMAC
- Review any changes in the subject's medical history or concomitant medication use since Screening
- Conduct targeted physical examination
- Obtain weight
- Obtain temperature and seated BP and PR
- Obtain 12-lead ECG
- Confirm and document that the subject continues to meet all eligibility criteria
- Randomize the subject

NOTE: Subjects may be randomized prior to the completion of the Day 1 procedures listed above if necessary to allow pharmacy staff sufficient time to prepare IP.

- Collect pre-dose synovial fluid sample for biospecimen banking (if the subject has consented to provide this optional sample)
- Administer KA34 or placebo
- Obtain temperature and seated BP and PR at 15 minutes, 30 minutes, 60 minutes, 90 minutes, 2 hours, and 4 hours after dosing
- Collect blood samples for PK analysis at 15 minutes, 30 minutes, 60 minutes, 90 minutes, 2 hours, and 4 hours after dosing
- Collect serum sample for biospecimen banking at 4 hours post-dosing (if the subject has consented to provide this optional sample)
- Assess adverse events starting at the time of IP administration by spontaneous reporting and by asking the subject to respond to a non-leading question such as "How do you feel?"
- Record any concomitant medications administered while the subject was at the study site
- Remind the subject about study contraception requirements (if applicable)

• Subjects may be discharged after at least 2 hours of safety observation following the last procedure

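### Criterion 1(d) admits women from age 40 on tubal ligation alone, and no scheduled test would detect a pregnancy before the first injection

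*Protocol*

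**What the plan says.** Protocol 4.1 and the protocol summary define non-childbearing potential by four alternatives, any one of which is enough:

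- 1(a): 12 months without menses and an FSH level in the postmenopausal range;
- 1(b): hysterectomy and/or removal of both ovaries;
- 1(c): confirmed ovarian failure;
- 1(d): "Have undergone a documented bilateral tubal ligation".

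The document history shows that 1(d) was added on purpose.

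Section 4.4, which is addressed to male subjects and covers their partners' methods, lists "Bilateral tubal ligation/bilateral salpingectomy or bilateral tubal occlusive procedure" among methods that "result in a failure rate of less than 1% per year when used consistently and correctly".

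At Screening (6.1), under "Collect blood and urine samples for the following", the plan names the safety laboratory tests, FSH for women and a urine drug test. On Day 1 (6.2.1 and 6.3.1) it says "Collect blood and urine samples for safety laboratory tests" and adds PK, PIIANP, CTX-II and optional banked samples. For timing, "All D1 pre-dose laboratory assessments should be conducted within 48 hours prior to IP administration". Table 1 in 7.1.1 lists FSH and the drug screen as the only other laboratory tests.

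SAP section 10 lists FSH, urine drug screen and contraception review data, but no pregnancy test. In the protocol, hCG occurs only in the abbreviation list. Section 4.2 does not name pregnancy as an exclusion.

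**The concern.** Criteria 1(a) to 1(c) describe women in whom pregnancy is effectively excluded. Criterion 1(d) describes women who are protected against it but may still ovulate and have a uterus. When 1(d) was added, the pre-dose checks were not extended to match.

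What is at stake is participant safety before first exposure. Section 8.4.2 requires exposure during pregnancy to be reported within 24 hours of awareness. Nothing scheduled would create that awareness in the one group of enrolled women where pregnancy remains possible.

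The plan is stricter on the paternal side. The note to criterion 1 requires condoms for men whose partner is pregnant or could become so, even after a confirmed vasectomy.

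Section 1.2.2 names general toxicity and genotoxicity studies but no reproductive study. The Investigator's Brochure, to which it refers, was not available for this review.

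**Working it through.** The plan gives no figure to reproduce. The check has two parts.

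**Text.** FSH is measured in all women at Screening, but the result is a condition only of 1(a), and FSH does not detect pregnancy. The safety laboratory tests are hematology, chemistry and urinalysis. The Screening list, both Day 1 lists, Table 1 and the multiple-dose schedule contain no pregnancy test. The single-dose schedule table is only partly legible in the text reviewed, but the procedure list in 6.2.1 is complete.

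**Size.** Inputs:

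- Annual rate r = 1%, the ceiling in 4.4 for the whole class of methods. It is not specific to ligation or to women over 40, so the true rate is probably lower.
- W = 42, 56 or 84 days from conception during which a pregnancy stays unrecognised (assumption).
- D = 10 or 14 days from conception until urine hCG turns positive (assumption).
- Share on KA34: 18/24 in the single-dose cohorts and 27/36 in the multiple-dose cohorts, both 0.75.

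For a woman eligible only under 1(d):

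- pregnant and unaware on Day 1 = r × W/365
- found by a Day 1 test = r × (W − D)/365
- missed by a Day 1 test = r × D/365
- found by a test on Day −28 only = r × max(0, W − 28 − D)/365

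| W (days) | Pregnant on Day 1 | Found on Day 1, D = 14 | Found on Day 1, D = 10 |
|---|---|---|---|
| 42 | 0.115% | 0.077% | 0.088% |
| 56 | 0.153% | 0.115% | 0.126% |
| 84 | 0.230% | 0.192% | 0.203% |

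- Missed on Day 1: 0.027% (D = 10) to 0.038% (D = 14).
- Share found: from 28/42 = 67% to 74/84 = 88%.
- Detectable, and would have received KA34: 0.75 × 0.077% = 0.058% to 0.75 × 0.203% = 0.152%.
- Screening test alone at Day −28: 0 to 0.011% for W = 42, and 0.115% to 0.126% for W = 84. It misses conceptions in the last 28 + 10 = 38 to 28 + 14 = 42 days before dosing.

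With a shorter assumed window of 28 to 56 days, the chance of being unknowingly pregnant on Day 1 is 0.01 × 28/365 = 0.08% to 0.01 × 56/365 = 0.15%, the same order of size. At an assumed rate of 0.1% per year, every percentage of women is ten times lower.

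The number of women who would enter under 1(d) is not stated. As an extreme bound, if all 60 or so subjects were such women, the expected number of detectable pregnancies exposed to KA34 would be 60 × 0.058% = 0.035 to 60 × 0.152% = 0.091.

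**The case against.** The strongest reply is that this was a deliberate choice and the risk is negligible. Under the protocol's own definition these women are not of childbearing potential. Section 4.4 is written for men and their partners and does not contradict 4.1. The expected number of exposed pregnancies is below one tenth even under the extreme bound. Systemic concern is also low: the route is intra-articular, the SAP (15.1) expects no quantifiable parent drug in plasma after 4 hours, genotoxicity tests were negative, and the IV/IA AUC margins in animals are 240-fold (rat) and 453-fold (dog).

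All of that stands, and it is why the point ranks low. It does not close the gap, because the exposure margins are for general toxicity and not for embryo-fetal effects.

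Other safeguards exist:

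- FSH in every woman;
- Day 1 review of history and eligibility;
- exclusion 18;
- unscheduled laboratory tests;
- withdrawal for safety under 6.4.

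FSH gives the investigator information on menopausal status but does not detect pregnancy. The others depend on someone suspecting pregnancy, and a documented ligation makes that less likely.

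Two further points are fair. A known pregnancy would arguably already fail inclusion 1 or exclusion 18, so a named exclusion mainly gives a positive test a clear consequence. And in this model a continuing pregnancy detectable at Screening is also detectable on Day 1, so the Screening test mainly gives earlier notice. The Imaging Manual for the Screening MRI was not available, so the absence of a test is established only for the protocol and SAP.

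**Conclusion.** The concern holds. Criterion 1(d) stands alone from age 40, and neither document schedules a test that would detect a pregnancy before the first injection. The size is small: at most 0.12% to 0.23% per woman eligible only under 1(d), given the 1% ceiling and a 42 to 84 day unrecognised period. A Day 1 test could prevent 0.06% to 0.15% per such woman from being exposed to KA34 while pregnant. These figures rest on assumed values of W and D and on a rate ceiling that probably overstates the truth; confidence in the size is moderate. It is a participant-safety point with no effect on any analysis, and is offered for consideration because the remedy is cheap.

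**What to change.** Keep 1(d). For women eligible only under it:

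1. Add an hCG test at Screening and a urine hCG test on Day 1, within the existing 48-hour pre-dose laboratory window. Read the Day 1 result before injection and, where possible, before randomisation, because 6.2.1 and 6.3.1 allow randomisation before the other Day 1 procedures are complete.
2. Enter both tests in Table 1, both schedules and sections 6.1, 6.2.1 and 6.3.1. The SAP section 10 listings should then name them.
3. Make a positive result an exclusion in 4.2 and in the protocol summary.

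If only one test is added, choose Day 1. Repeats on Days 8, 15 and 22 are optional and not part of this request. On Days 15 and 22 they would need a separate or split urine sample, since only the CTX-II sample is scheduled then and its handling is controlled (7.3). No new stopping rule is needed.

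The cost is two inexpensive assays per such woman, on blood and urine already collected. An unclear result could briefly delay Day 1. A positive result read after randomisation would use a slot, which 6.4 allows to be replaced. Sample size, visits and statistical methods do not change.
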